#### 4. LIST OF ABBREVIATIONS

ACE	angiotensin-converting enzyme
ACR	American College of Rheumatology
AE	adverse event
ALT	alanine aminotransferase
APAP	acetaminophen
ARB	angiotensin receptor blocker
ASA	acetyl salicylic acid
AST	aspartate aminotransferase
ATC	Anatomical Therapeutic Chemical
BMI	body mass index
COX	cyclooxygenase
CRA	clinical research associate
CRO	contract research organization
CSR	clinical study report
████████	████████
ECG	Electrocardiogram
eCOA	Electronic Clinical Outcome Assessment
eCRF	electronic case report form
EDC	electronic data capture
eDiary	electronic diary
ET	Early Termination
FDA	Food and Drug Administration
GCP	Good Clinical Practice
GI	Gastrointestinal
IB	Investigator's Brochure
ICF	informed consent form
ICH	International Council for Harmonisation of Technical Requirements for Pharmaceuticals for Human Use
IP	investigational product
IRB	institutional review board
ITT	intent-to-treat
IUD	intrauterine device
IWRS	interactive web response system
LK	Likert
MAR	missing at random
MedDRA	Medical Dictionary for Regulatory Activities
MMRM	mixed model repeated measures
MNAR	missing not at random
NRS	numeric rating scale
NSAID	nonsteroidal anti-inflammatory drug
OA	Osteoarthritis
OAKHQOL	OA Knee and Hip QOL
OTC	over the counter
PGA	Patient Global Assessment
PGIC	Patient Global Impression of Change
PK	Pharmacokinetics
PMM	Pattern Mixture Model
PRP	platelet rich plasma
QOL	Quality of Life
QTcF	QT interval corrected for heart rate (Fridericia's correction)

---

SAE	serious adverse event
SAF	safety analysis set
SAP	statistical analysis plan
SD	standard deviation
SOC	standard of care
ULN	upper limit of normal
US	United States
WHO-DD	World Health Organization Drug Dictionary
WOMAC	West Ontario and McMasters Universities Osteoarthritis Index

## 5. INTRODUCTION

### 5.1. Background and Rationale

An estimated 52.5 million adults (22.7% of the population) in the United States (US) have physician-diagnosed osteoarthritis (OA); 22.7 million (9.8% of all adults) have arthritis and arthritis-attributable activity limitations. Based on these data, it is projected that 78 million (26%) adults aged 18 years or older will have physician-diagnosed arthritis by the year 2040. Patients with arthritis are encouraged to be active, since it has been shown that exercise and activity help to decrease pain associated with OA, improve function, and delay disability. However, activity and exercise are often limited by the pain associated with arthritis, and this pain may become part of a cycle of inactivity and weight gain that tends to perpetuate the stiffness and disability associated with OA. Additionally, oral nonsteroidal anti-inflammatory drug (NSAID) medications used over time may cause gastrointestinal (GI) distress and interfere with the blood-clotting cycle. Opioid medications often lose their effectiveness with chronic use and require increasing dosages; patients may also become dependent on the opioid pain relievers, thereby introducing additional health problems and increasing disease and healthcare system burden. There is an unmet need for safer, reliable, and effective pain medications without the safety risk and limited efficacy associated with those currently available.

Diclofenac sodium belongs to the phenylacetic acid class of NSAIDs developed by Ciba Geigy Co., Ltd., Switzerland, in 1965. In the US, diclofenac sodium is available in various dosage forms, including tablet, eye drop, extended-release tablet, gel, patch, capsule, and solution. The mechanism of action of NSAIDs is not completely understood but thought to be related to prostaglandin synthetase (cyclooxygenase [COX]-1 and COX-2) inhibition.

Noven Pharmaceuticals, Inc. is developing a formulation of diclofenac sodium for topical administration, the HP-5000 topical system (patch) for the treatment of pain of OA of the knee(s). The topical HP-5000 patch will provide patients with OA with another treatment option that may have potential benefits compared with the existing formulations, as follows:

- Delivery of drug into the treatment target area resulting in lower systemic and GI exposure when compared with orally administered diclofenac sodium and a possible reduction of systemic side effects including GI ulcers/lesions and adverse reactions such as nausea, vomiting, dyspepsia, and stomach pain.
- Improvement of compliance with [REDACTED] compared with existing topical formulations and use by patients who have difficulty swallowing oral preparations.

## 5.2. Clinical Experience

To date, the HP-5000 development program includes

These studies have been completed with various formulations of HP-5000, evaluating the pharmacokinetics (PK) and tolerability in healthy volunteers and efficacy and safety in subjects with OA pain of the knee. The lead formulation for this program, HP-5000, which contains mg diclofenac sodium with a patch size of cm^2, was selected based on the efficacy, safety, PK profile, and patch performance characteristics.

The HP-5000 [REDACTED] formulation is being developed in Japan by Noven's parent company,

for different indications

[figure not shown]
and is referred to as the

The Phase 1 study that evaluated PK and safety for the current formulation (HP-5000 [REDACTED]) in healthy volunteers was as follows:

1

The Phase 2 efficacy and safety study performed in the US on patients with OA pain of the knee is as follows:

1

Data across these studies demonstrated an acceptable performance, safety and tolerability profile for HP-5000 [REDACTED].

Hereinafter, HP-5000 [REDACTED] is referred as HP-5000 in this protocol. Further details about HP-5000 development and detailed information are available in the Investigator's Brochure (IB).

### **5.3. Summary of Potential Risks and Benefits**

The HP-5000 formulations have been studied in a number of PK studies and most recently in a large randomized, placebo-controlled Phase 2 efficacy and safety study in the US among subjects with pain of OA of the knee [REDACTED]. The PK studies revealed a PK profile supportive of topical use via transdermal route. The Phase 2 study demonstrated significant reduction in pain by Week 4 compared with placebo with a favorable systemic safety profile and good dermal tolerability with HP-5000 [REDACTED] formulation. The potential benefits for subjects of study participation are the following: (1) may experience a reduction in pain and inflammation as a result of treatment with the HP-5000 patch, (2) may experience improvement in their physical function and stiffness, and (3) will contribute to the scientific knowledge and therapeutic advancement in OA disease state that may lead to expansion of future treatment options for subjects with OA.

The potential risks for subjects for participating in study include those associated with exposure to the HP-5000 patch and the risks inherent in medical evaluation, including venipunctures at various times in study.

A summary of the pharmaceutical properties and known potential risks of the HP-5000 patch are provided in the current version of the IB. The investigator(s) must become familiar with all sections of the HP-5000 IB.

## 6. OBJECTIVES

### 6.1. Primary Objectives

- To evaluate the effect of HP-5000 on pain among subjects with OA of the knees at Week 12.

### 6.2. Key Secondary Objectives

- To evaluate the effect of HP-5000 on physical function among subjects with OA of the knees at Week 12.
- To evaluate the effect of HP-5000 on stiffness among subjects with OA of the knees at Week 12.

### 6.3. Other Secondary Objectives

- To evaluate the effect of HP-5000 on pain among subjects with OA of the knees at Weeks 1, 2, 4, and 8.
- To evaluate the effect of HP-5000 on physical function among subjects with OA of the knees at Weeks 1, 2, 4, and 8.
- To evaluate the effect of HP-5000 on stiffness among subjects with OA of the knees at Weeks 1, 2, 4, and 8.
- To evaluate the effect of HP-5000 on pain intensity as measured by numeric rating scale (NRS) scores on a daily diary.
- To evaluate the onset of effect of HP-5000 on pain among subjects with OA of the knees.
- To evaluate the pattern of use of rescue medication in the study.
- To evaluate skin irritation, discomfort, and adhesion following administration of HP-5000.
- To evaluate the safety and tolerability of HP-5000.
- To evaluate the effect of HP-5000 treatment on Quality of Life (QOL).

## 7. STUDY DESIGN

Note: Pandemic-related restrictions may result in difficulties regarding the conduct of the study. If circumstances require it, a protocol amendment may be created to document changes to some aspects of the study, such as inclusion/exclusion criteria, visit windows, visit schedules, the possibility of remote (rather than on site) visits, and distribution of study drug.

### 7.1. Overall Study Design and Plan - Description

This is a multicenter, randomized, double-blind, placebo-controlled Phase 3 study in the US evaluating the efficacy and safety of HP-5000 in subjects with OA pain of the knees.

The study will consist of up to a 28-day Screening Phase that will include a Washout Period of current prescription and over the counter (OTC) analgesics; a 12-week Double-blind Treatment Phase, and a 1-week safety Follow-up Phase.

[figure not shown]
- **Screening Phase:** Subjects will be seen in the clinic where the study will be described to them and will be asked to sign the informed consent form (ICF). No screening procedures may begin prior to obtaining informed consent. After obtaining a written informed consent, subjects will be screened for participation in the study. The target knee for the purpose of the study will be defined as the one which causes the subject more pain than the other knee and will be identified at Screening visit using the NRS score. During the Screening Phase, subjects will complete a daily electronic diary (eDiary) to record pain severity of their target knee. Subjects who satisfy the entry criteria at Screening and Washout visit will be instructed to begin the Washout Period for 7 to 14 days, or at least 5 half-lives, whichever is longer, prior to the Baseline Visit (Day 0).

During the Washout Period, current prescription and OTC analgesics will be discontinued. However, rescue medication (acetaminophen [APAP]) for the treatment of the target knee pain of OA because of lack of efficacy of study drug (not for the non-target knee) if the subject does not feel enough pain relief by the study drug, any other aches the subject might experience during the trial, such as headache and reduction of fever will be permitted (a maximum of 2 g/day) except within 3 calendar days prior to the Baseline Visit (i.e., rescue medication is prohibited for 2 days until clinic visit on Day 0 and on the day of Baseline Visit [V3]). Subjects should not use OTC APAP as rescue medication, i.e., they should only use the APAP provided by the Sponsor or designee. During the Washout Period, subjects will complete a daily eDiary to record rescue medication usage in addition to pain severity of their target knee. Following completion of the Washout Period, subjects will return to the clinic for their Baseline Visit (Day 0). Eligible subjects will be randomized to either HP-5000 or placebo in a 1:1 ratio.

- **Double-blind Treatment Phase:** Subjects will apply a single patch to the target knee [REDACTED] After the removal of the patch [REDACTED] [REDACTED] a new patch will be applied to a different site on the target knee. Subjects will be instructed to rotate the patch application site [REDACTED] to alternate sides (inner and outer) of the target knee. During the Double-blind Treatment Phase, subjects will also complete a [REDACTED] eDiary to record patch application and removal time, adhesion, irritation, discomfort, and pain assessments; and amount of rescue medication (APAP) taken daily, if applicable. A maximum of 2 g/day of APAP will be allowed as rescue medication except from Baseline Visit until Visit 4, within 2 calendar days prior to all subsequent visits (V5, V6, V7, and V8), and on the day of the clinic visits (V4, V5, V6, V7, and V8). Subjects should not use OTC APAP as rescue medication, i.e., they should only use the APAP provided by the Sponsor or designee.

NOTE: Subjects are NOT allowed to apply HP-5000 on the non-target knee at any time during the study.

- **Follow-up Phase:** Subjects will have a safety visit approximately 7 days after the Week 12 End-of-Treatment Visit. The investigator or qualified study staff will contact all subjects by phone for continued safety monitoring of adverse events (AEs). At the discretion of the investigator, subjects may have to return to the clinic for their Follow-up Visit.

**Figure 1** A Schematic of the Study Design

## 7.2. Discussion of Study Design

This is a multicenter, randomized, double-blind, placebo-controlled Phase 3 study evaluating the efficacy and safety of HP-5000 in subjects with OA pain of the knees. Such a design is well accepted and considered standard in drug development when evaluating new therapeutic modalities across different disease areas.

A parallel-group design was selected because it is free of the assumptions underlying competing designs (for example, crossover). A parallel-group approach is considered the optimal study design to evaluate efficacy in pivotal registration clinical trials.

The use of a randomized double-blind design will minimize bias by randomly assigning the subjects to treatment arms, and ensuring that the subjects, investigators and site personnel, and the Sponsor/designee are blinded to the treatment allocations.

A placebo control will be used to allow for an unbiased assessment of treatment effects and safety data. The comparison with placebo is justified as subjects will be closely monitored and study treatment will be discontinued and the subject will be returned to standard of care (SOC) treatment if their status deteriorates.

The rationale for dose selection is described in [Section 9.6](#).

The 12-week duration is considered to be sufficient to evaluate the effect on chronic pain of OA. This time period is also sufficient to evaluate changes in the primary and secondary outcome measures.

The use of rescue medication is prohibited within 3 calendar days prior to the Baseline Visit, on the day of Baseline Visit (V3), from Baseline Visit until Visit 4, within 2 calendar days prior to all subsequent visits (V5, V6, V7, and V8), and on the day of the clinic visits (V4, V5, V6, V7, and V8), thus ensuring the integrity of the pain assessments and safeguarding against confounding due to rescue medications.

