### **8.2.3 Premature Subject Withdrawal**

All subjects are free to withdraw from participation in the study at any time, for any reason, specified or unspecified, and without prejudice to further treatment. The criteria for enrollment are to be followed explicitly and if a subject who does not meet enrollment criteria is inadvertently enrolled, that subject should be withdrawn from the study and the Sponsor or CRO must be notified.

Subjects should not be asked to withdraw from the study because of experiencing AE, lack of efficacy, pregnancy, or lack of compliance to the clinical study protocol, etc. Those patients can stop their study treatments (for subjects who do not comply the protocol specified instructions and procedures, every effort will be made to keep them in the study after stopping treatment unless there is an adverse impact on subject safety). Discontinuation from study treatment does not automatically lead to a complete withdrawal from the study. Subjects discontinuing from study treatment are strongly encouraged to continue in the study up to the study completion (Follow-up Phone Visit, Week 13).

Subjects who decide they do not wish to remain in the study should NOT be considered withdrawn from the study UNLESS they withdraw their consent. Subjects are encouraged to return to all scheduled site and telephone visits, perform all procedures (including eDiary completion and blood draws) and follow the all requirements of the protocol (including the prohibited therapies), but without study treatment administration, until the end of the study (Follow-up Phone Visit, Week 13).

The reason for study treatment discontinuation and withdrawal from the study will be separately recorded. When the subject discontinues study treatment and/or withdraw from the study, the reason will be recorded in the medical records and eCRF using the below categories for discontinuation of study treatment and withdrawal from the study respectively.

The reasons will be grouped into three main categories: “study treatment related”, “not study treatment related”, and “uncertain” and more specific sub-categories will be described under each of the three main categories.

- Study treatment related
  - Lack of efficacy
  - Adverse events
  - Deviation from protocol (Please specify the deviation)
  - Other
- Not study treatment related
  - Adverse events
  - Prohibited Medication Use
  - Pregnancy
  - Deviation from protocol (Please specify the deviation)
  - COVID-19

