**Table 2 Prohibited Medications/Therapies**

Prohibited Medications/Therapies	Conditions
Any nonsteroidal anti-inflammatory drugs (NSAIDs) (selective or nonselective [Topical drug not for knees will be allowed]), acetaminophen (APAP) (>2 g/day), aspirin (ASA) (>81 mg/day), anticonvulsants (i.e., pregabalin and gabapentin etc.), muscle relaxants, other oral analgesics (prescription and/or over the counter [OTC]), antidepressants prescribed for the control of chronic pain syndromes, antihistamine with a sedative effect, sedatives for insomnia, topical products on the knee including methyl salicylate, camphor, menthol, methylsulfonylmethane, [REDACTED] [REDACTED] [REDACTED] capsaicin, any nonpharmaceutical therapy to relieve knee pain (physiotherapy, massage therapy, hot wax therapy, ice pack, acupuncture, thermal modalities, radiofrequency ablation, transcutaneous electrical nerve stimulation [TENS], pulsed vibration therapy, etc.), device to relieve knee pain (biofemoral bracing, kinesiotaping, modified shoes, wedged insoles etc.), hydroxychloroquine.	Prohibited during the study starting at Washout Visit
Any opioids, cannabinoids (prescribed or used recreationally), corticosteroids including oral, intra-muscular and intra-articular, topical, inhalation (a stable dose by inhalation for seasonal allergies and/or topical use for dermatologic allergies are allowed [Not allowed on the knees]), intra-articular viscosupplementation (e.g., Synvisc®), intra-articular drugs/biologics; anti-nerve growth factor agents, platelet rich plasma (PRP) injection, stem cells, prolotherapy, amniotic fluid injection, cyclosporine, lithium, or methotrexate	Prohibited during the study starting at Screening Visit
MAJOR SURGERY: Surgery to the target knee (i.e., damage/reconstruction of the anterior or posterior cruciate ligaments).  MINOR SURGERY: Surgery to the target knee defined as anything other than major surgery (as defined above)	Prohibited during the study starting at Screening Visit

Note: The investigator should contact the Medical Monitor with any concerns about the acceptability of any medication.

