## 9.11. Rescue Medication

If needed, subjects will be allowed to take up to a maximum of 2 g (4 × 500 mg tablets) of oral APAP per day (as provided by the Sponsor or designee) as rescue medication for the treatment of the target knee pain of OA because of lack of efficacy of study drug (not for the non-target knee) if the subject does not feel enough pain relief by the study drug and any other aches they might experience during the trial such as headache and reduction of fever except within 3 calendar days prior to the Baseline Visit, on the day of Baseline Visit (V3), from Baseline Visit until Visit 4, within 2 calendar days prior to all subsequent visits (V5, V6, V7, and V8), and on the day of the clinic visits (V4, V5, V6, V7, and V8). Information regarding the use of rescue medication, such as the number of tablets taken, the time when it was taken, and the reason of use, will be recorded on the eDiary. Subjects should not use OTC APAP as rescue medication, i.e., they should only use the APAP provided by the Sponsor or designee. Rescue medication will be labeled appropriately for the study to ensure visual difference from similar OTC medications and to ensure proper understanding the rescue medication should be used for this study. NSAIDs or any other analgesics except study drug and rescue medication provided will not be permitted from the time that informed consent form is signed until study completion or early termination. Stable low doses of ASA up to 81 mg/day will be allowed.

Subjects are **NOT** allowed to apply study treatment drug (HP-5000/Placebo) on the non-target knee at any time during the Double-blind Treatment Phase.

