**Note: After Visit 8, subjects may resume their standard of care treatment.**

#### **10.1.4 Follow-up Phase**

A follow-up phone Visit will take place approximately 7 days after Visit 8 (or Early Termination Visit), and will include the following assessment and procedures:

1. Review subject's use of concomitant medications.
2. Review AEs.
3. Record the findings in the eCRF.

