### **11.2.4 Treatment of Adverse Events**

Adverse events that occur during the study will be treated, as necessary, by established standards of care. If such treatment constitutes a deviation from the protocol, the subject should be withdrawn from the study and the reason and date of withdrawal must be documented in the eCRF. The decision about whether the subject may continue in the study will be made by the sponsor after consultation with the investigator and/or Medical Monitor.

If a subject experiences an intolerable AE , the investigator must decide whether to withdraw the subject from the study and/or treat the subject. Special procedures may be recommended for the specific study drug, such as the collection of a serum sample for determining blood concentrations of study drug, or treatment regimens, as appropriate.

It is **NOT** necessary to unblind a subject’s treatment assignment in most circumstances, even if an SAE has occurred. If unblinding is necessary, see **Section 9.5** for a description of the unblinding procedures.

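### Protocol section 11.2.4 still makes study withdrawal the default when treatment of an adverse event deviates from the protocol, out of line with amended section 8.2.3; section 7.2 should also say how a subject gets back to standard of care

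*Protocol*

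**What the plan says.** All references are to the amended protocol (the second of the two copies), which I take to be the version 2.0 that SAP section 1 follows.

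- **Section 8.2.3** treats stopping study treatment and leaving the study as two events with separately recorded reasons. It says: "Subjects should not be asked to withdraw from the study because of experiencing AE, lack of efficacy, pregnancy, or lack of compliance". For subjects who do not comply, "every effort will be made to keep them in the study after stopping treatment unless there is an adverse impact on subject safety". Someone who stops the patch and stays is encouraged to "follow the all requirements of the protocol (including the prohibited therapies), but without study treatment administration, until the end of the study".
- **Section 11.2.4, first paragraph**, says AEs are treated by established standards of care, then: "If such treatment constitutes a deviation from the protocol, the subject should be withdrawn from the study". The next sentence gives the decision on continuation to the sponsor, after consultation.
- **Section 11.2.4, second paragraph**, covers an intolerable AE. The investigator chooses between study withdrawal, treatment, or both. Stopping only the patch is not offered.
- **Section 7.2** rests the use of placebo partly on this: "study treatment will be discontinued and the subject will be returned to standard of care (SOC) treatment if their status deteriorates".
- **Section 9.11** says that NSAIDs and other analgesics, apart from study drug and the supplied rescue, "will not be permitted from the time that informed consent form is signed until study completion or early termination". **Table 2**, first row, includes NSAIDs and reads "Prohibited during the study starting at Washout Visit". Neither has an exception for a subject who is off the patch.
- The note between the Visit 8 procedures and section 10.1.4 says: "After Visit 8, subjects may resume their standard of care treatment".
- **Section 8.2.1, criterion 2d**, requires stable oral or topical NSAID therapy at entry, so usual care in this population is NSAID-based.

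**The concern.** The amended 8.2.3 adopts retention: stop the patch if need be, but keep the subject and the visits. Section 11.2.4 is where a site looks when it is managing an AE, and it still points to the exit. A subject who needs a Table 2 drug for an AE, perhaps while still wearing the patch, can be taken out of the study under 11.2.4 although 8.2.3 would keep that subject. The result is avoidable withdrawals and missing data.

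The second, smaller matter is that 7.2 does not say how the promised return to standard of care is reached. For a subject who stops the patch and stays, the NSAID ban continues. A reader of 7.2 alone would not know that permitted NSAID care before Visit 8 generally means leaving the study.

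**Working it through.** **Step 1: the two withdrawal rules side by side.**

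| Situation | Section 11.2.4 | Section 8.2.3 |
|---|---|---|
| AE treated with a permitted drug | Treat; no withdrawal trigger | Do not ask for withdrawal |
| AE treated with a Table 2 drug | Default is study withdrawal; sponsor decides on continuation | Do not ask for withdrawal because of an AE or non-compliance; may stop the patch and stay |
| Intolerable AE | Study withdrawal and/or treatment | May stop the patch and stay |

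The first row agrees; the other two do not. The second row is realistic. Table 2 bars topical corticosteroids on the knee, sedating antihistamines and muscle relaxants, so ordinary treatment of an application-site reaction or a strain could trigger the default.

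The rest of the plan follows 8.2.3. Section 11.2.2.3 has action codes for withdrawing or interrupting the drug. SAP section 18.1.2 identifies AEs that stop study medication separately from AEs that end participation.

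**Step 2: what one avoidable withdrawal costs, and how long the NSAID ban lasts for a subject who stays.** Inputs from protocol sections 10.1.3 and 10.2: WOMAC and vital signs at target Days 7, 14, 28, 56 and 84; laboratory tests after baseline at Days 28 and 84; Visit 8 at Day 84 with a window of ±7 days. For a withdrawal or stop on Day d:

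- assessments lost = scheduled days later than d, up to Day 84;
- NSAID gap to Visit 8 = 84 − d, range (77 − d) to (91 − d).

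| Day d | WOMAC lost | Vital signs lost | Laboratory lost | NSAID gap if retained, days (range) |
|---|---|---|---|---|
| 7 | 4 | 4 | 2 | 84 − 7 = 77 (70 to 84) |
| 14 | 3 | 3 | 2 | 84 − 14 = 70 (63 to 77) |
| 28 | 2 | 2 | 1 | 84 − 28 = 56 (49 to 63) |
| 56 | 1 | 1 | 1 | 84 − 56 = 28 (21 to 35) |

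The early termination visit adds one set of assessments at exit. Under SAP Table A it can stand for Week 12 only if it falls 74 days or more after Day 0.

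**Step 3: where the loss falls.**

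- *Still on the patch, AE treated with a Table 2 drug.* If kept, the Week 12 score enters the primary mixed model unless another intercurrent event applies. If withdrawn, it is missing and rests on the missing-at-random assumption.
- *Patch stopped for a treatment-related reason.* Benefit is set to zero from that time (protocol 13.4.3.1, SAP 16.1.4), so the primary analysis depends little on later scores.
- *Patch stopped for another reason.* Scores more than 24 hours after removal are left out of the primary analysis.
- *Both stop groups.* Later data still feed the supplementary analysis without intercurrent-event adjustment (SAP 16.1.6), the other secondary analyses (16.3) and the by-visit safety summaries (18.3, 18.5).

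**The case against.** The strongest reply on 11.2.4 is that the triggers differ. Section 8.2.3 speaks of the AE itself; 11.2.4 speaks of AE treatment that breaks a protocol rule, and it names the sponsor as decision-maker. That is fair, and the two texts are not flat opposites. But 8.2.3 also covers non-compliance, which is what such treatment amounts to. A default with an override is still a default, and the second paragraph of 11.2.4 leaves out the option on which 8.2.3 is built.

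A reader might infer from 7.2 that a deteriorating subject has no route to standard of care before Visit 8, and so that placebo is unjustified. The documents do not support that. Section 8.2.3 lets subjects leave at any time without prejudice to further treatment and only encourages staying, and 9.11 ends its ban at early termination. Section 11.1.1 counts worsening of a pre-existing condition as an AE, and 11.2.4 has AEs treated by standards of care. An NSAID given that way would still be a deviation, and the 11.2.4 default would then apply, so this route leads back to the main point.

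A reader might also count the days without any analgesic against the retained subject. Acetaminophen up to 2 g/day remains available, and its blackout days around visits apply equally to subjects still on the patch.

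Finally, one might conclude that the NSAID ban should be lifted after a stop. The ban keeps standard-of-care NSAIDs out of the unadjusted efficacy analyses and the by-visit laboratory and vital-sign summaries. Keeping it is a legitimate choice, and lifting it is a trade-off. It does not correct an error.

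**Conclusion.** The point holds and is minor. Section 11.2.4 was not aligned with amended 8.2.3. Followed as written, its default would produce study withdrawals that 8.2.3 aims to avoid, at a cost of 1 to 4 scheduled WOMAC assessments per subject for exits from Day 56 back to Day 7. Section 7.2 is incomplete: for a subject who stops the patch and stays, permitted NSAID care waits until Visit 8 (28 to 77 days on target days for the same stops) unless the subject terminates early.

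This assumes visits on target days, except where the Visit 8 window is shown, and that the specific note after Visit 8 overrides the Week 13 wording of 8.2.3. The documents give no rate of treatment stops or of AEs needing a Table 2 drug, so the number of subjects cannot be stated. Nothing here shows bias in the primary comparison or makes the placebo control improper.

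**What to change.** 1. **Section 11.2.4, first paragraph.** Replace the withdrawal clause with: *the subject should be kept in the study, with study treatment stopped if the investigator and Medical Monitor judge it necessary.*
2. **Section 11.2.4, second paragraph.** Make the investigator's choice *whether to stop study treatment and/or treat the subject*, with study withdrawal only on withdrawal of consent or for subject safety, in line with 8.2.3.
3. **Section 7.2.** Add: *Return to SOC analgesics requires early termination or completion of Visit 8.* This describes permitted care; an NSAID given to treat an AE under 11.2.4 would remain a recorded deviation.
4. Leave the prohibited-therapy rules for retained subjects in 8.2.3, 9.11 and Table 2 as they are.

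The cost is three wording changes in two protocol sections, with no added visits, subjects or data and no change to the SAP's analysis rules. One consequence should be accepted knowingly: some retained scores will be taken under a Table 2 drug. Such use is not among the intercurrent events in SAP section 2.4, so for a subject still on the patch those scores would enter as observed. That is already the position for non-compliers kept under 8.2.3, and the deviation reporting in SAP section 9.1 makes these subjects identifiable.
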